12. STATISTICAL METHODS

A Statistical Analysis Plan (SAP) will be prepared and finalized before unblinding for the first interim analysis. Any deviations from the final SAP will be described and justified in the study report. All statistical analyses will be performed using SAS[®].

Descriptive statistics, including the numbers and percentages for categorical variables, and the numbers, means, standard deviations, medians, minimums, and maximums for continuous variables, will be provided. All data will be summarized separately by dose level and study drug (CD388 Injection or placebo). Listings of individual subject data will also be produced.

Safety, tolerability, and PK will be summarized using descriptive statistics. There will be no formal hypothesis testing.

12.1. Analysis Populations

Analysis populations are:

- Safety Population: all subjects who receive any amount of study drug
- PK Analysis Population: all subjects who receive CD388 Injection and who have any blood samples analyzed

12.2. Analysis of Study Population and Subject Characteristics

Demographics (including age, race, ethnicity, and gender), baseline assessments (including height, weight, and BMI), medical history, and administration of study drug will be summarized for the Safety Population.

12.3. Safety Analyses

Safety will be evaluated by presenting summaries of AEs and SAEs, ECGs, clinical laboratory evaluations (hematology, coagulation, serum chemistry, urinalysis), and vital signs. Adverse events will be coded using the Medical Dictionary for Regulatory Activities (MedDRA). The incidence of TEAEs and AESIs will be presented by System Organ Class (SOC) and Preferred Term (PT), relationship to study drug, and severity. A TEAE is defined as an AE that emerges during or after study drug administration having been absent pre-treatment, or worsens relative to the pre-treatment state, and through the final study visit. In addition, the incidence of serious TEAEs and TEAEs leading to discontinuation of study drug or from the study will be presented by SOC and PT.

Descriptive statistics for clinical laboratory test results, ECG parameters, and vital signs, and for changes from Baseline, will be presented by time point. The incidences of potentially clinically significant (PCS) clinical laboratory results, ECG parameters, and vital signs will also be summarized by time point.

A summary of the injection site evaluation will be presented. The number and percentage of subjects with any local reaction will be provided, as will the number and percentage of subjects with pain, tenderness, erythema/redness, and induration/swelling. The severity of each local reaction will also be presented.

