1.1. Schedule of Events

Table 1: Schedule of Events

	Screening		Clinica	al Resea	Clinical Research Unit (CRU) Inpatient Stay	(CRU) I	npatient	Stay			Outpa	Outpatient CRU Visits	tU Visit	20
Day (Window)	-28 to -2	-1	1	2	3–6	L	6	11	14	30 (±3)	45 (±3)	(5±)	90 (±7)	120/165 a (±14)
Informed consent	X													
Inclusion/Exclusion criteria	X	X												
Medical history/demographics	X													
Complete physical with vital signs (BP, RR, HR, oral temperature, height, weight, BMI)	X													
Targeted physical with vital signs (BP, RR, HR, oral temperature, weight ^b)		×	×°	×	X	X			×	X	X	×	×	×
Safety ECG ^d	X	X	X			X			×	X				X
Laboratory evaluations (CBC with platelets, coagulation, serum chemistry, lipids, urinalysis)	X	X		X	X e	X			X	X	X	X	X	×
Virology screening (HBV, HCV, HIV)	X													
Virology screening (SARS-CoV-2)		×												
Serum/urine pregnancy test f	X	X								X		×	X	X
FSH (if applicable to confirm postmenopausal status)	X													
Drug/alcohol screen 8	X	X												
Randomization			X											
Dosing of study drug			X											
Reactogenicity/injection site inspection h			X	X	X									
PK sample collection i			X	X	X	X	X	X	X	X	X	X	X	X
Pharmacogenomics blood sample ^j			predose											
Exploratory biomarker samples			predose		X e									
Anti-drug antibodies			predose						X	X	X	X	X	X
Nasopharyngeal swab collection ^k			predose	X	X	X	X	X	X	X				
Assess and record AEs ¹	→													↑
Concomitant medications/procedures review m	\													↑

[figure not shown]
research unit; DAR = drug-antibody ratio; ECG = electrocardiogram; FSH = folliele-stimulating hormone; HBV = hepatitis B virus; HCV = hepatitis C virus; HIV = human Abbreviations: AEs = adverse events; BMI = body mass index; BP = blood pressure, CBC = complete blood count; COVID-19 = coronavirus disease 2019; CRU = clinical immunodeficiency virus; HR = heart rate; hr = hour; ICF = informed consent form; PK = pharmacokinetic; RR = respiration rate; SARS-CoV-2 = severe acute respiratory syndrome coronavirus 2.

Schedule of Events (continued)

- The timing of this visit is Day 120 for Cohort 1 and Day 165 for Cohorts 2 and 3. For subjects who discontinue study early, the Day 120/165 procedures should be performed.
- b. Weight should be measured at each of the outpatient visits (Days 30, 45, 60, 90, 120/165).

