- On Day 1, the targeted physical examination should be performed predose. Vital signs collection will occur predose, 6 hours postdose, and as clinically indicated, and will be measured with the subject in a seated position for at least 3 minutes prior to measurement. ပ
- A triplicate 12-lead ECG is to be performed at screening, at CRU check-in on Day -1, predose (immediately prior to study drug administration) and 6 hours postdose (±10 minutes) on Day 1, and as indicated in the schedule. Subjects are to be resting (at least 5 minutes) and semi-recumbent when ECG is being conducted. d.
- Laboratory evaluations (including exploratory biomarker samples) need to be performed once during the Day 3-6 interval on Day 4. e.
- A sensitive serum pregnancy test (\(\beta\)-human chorionic gonadotropin) is required at screening and Day 120/165 for females of childbearing potential. Urine pregnancy test may be performed at all other time points. £.
- Drug and alcohol screen is to be performed during the outpatient visits if vital signs are abnormal (see Appendix 2). ьio
- and once approximately 8-12 hours postdose, then twice daily on other indicated study days at least 6 hours apart), with any abnormal findings reported as At indicated visits, inspection of administration site and surrounding area will be performed twice daily (once between approximately 2-4 hours postdose, AEs. Reactions will be rated according to the scale provided in Table 5. þ.
- Blood samples for PK analysis will be collected predose (-24 hour window); post-dose at 2, 4, and 12 hours (each ±10 minute window); 24 hours (±30 minute window); 48 hours (±1 hour window); 72, 96, 120 hours (each ±2 hour window); and in the morning on Days 7, 9, 11, 14. Postdose samples collected at outpatient CRU visits at Days 30, 45, 60, 90, and 120/165 have the same windows (i.e., in ±days) as the visits. . 🚅
- A mandatory pharmacogenomic (DNA) blood sample will be collected once, preferably on Day 1 (collection at another time point is allowed if necessary) to allow for pharmacogenomic research related to CD388. ..
- Nasopharyngeal swab samples will be collected predose on Day 1, and on Days 2, 5, 7, 9, 11, 14, and 30. 7
- Adverse events (including influenza-like illness which will be tested for both COVID-19 and flu) will be collected for all subjects from the time of signing the ICF through the final study visit.

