6. STUDY DESIGN

6.1. Description of the Study

This is a Phase 1, single-center, prospective, randomized, double-blind study of ascending single doses of CD388 Injection administered SQ to healthy Japanese adult subjects. The goals are to assess safety, tolerability, and PK of CD388.

Subjects will be randomized to receive a single dose of CD388 or placebo administered via SQ injection (treatment assignment is blinded) according to the design in Table 3.

Table 3: Study Design

Number of Subjects (N = 27)				
Cohort: dose	CD388 (n = 21)	Placebo (n = 6)		
Cohort 1: 50 mg	7	2		
Cohort 2: 150 mg	7	2		
Cohort 3: 450 mg	7	2		

Note: A subject may not receive treatment in more than one cohort.

After 50% of Cohort 1 subjects have completed study drug administration and have undergone protocol-specified procedures and assessments for ≥10 days, the Principal Investigator (PI) and Sponsor will review blinded safety data: AEs (including systemic reactogenicity/injection site reactions, hypersensitivity reactions, and adverse events of special interest [AESIs]), vital signs, 12-lead ECGs, and clinical laboratory results (hematology, coagulation, serum chemistry, urinalysis) to determine the safety and tolerability of the study drug. The incidence and severity of AEs, and any adverse changes in vital signs, clinical laboratory findings, and ECGs will be considered when determining safety and tolerability of study drug. If the dose is determined to be safe and well tolerated ≥10 days after dosing, Cohort 2 will be enrolled. Enrollment of the remaining 50% of Cohort 1 will continue while the safety data of the first 50% of Cohort 1 is being reviewed. Similar processes will be followed for dose escalation from Cohort 2 to Cohort 3.

The Schedule of Events is presented in Table 1. All subjects will be admitted to the clinical research unit (CRU) for observation and safety assessments from Day -1 (check-in) to Day 14. Subjects will be monitored for AEs (including systemic reactogenicity/injection site reactions, hypersensitivity reactions, and AESIs) and SAEs throughout the study until the final study visit after dosing. Safety will also be assessed by physical examinations, ECGs, vital signs measurements, and laboratory evaluations (hematology, coagulation, serum chemistry, urinalysis) at various time points during and after the CRU stay. Concomitant medication use will be recorded throughout the study.

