Blood samples for PK and ADA assessments will be collected throughout the study. To maintain the blind, samples will be collected from all subjects; however, only samples from the CD388 Injection group will be analyzed (using validated assays) by an unblinded central bioanalytical laboratory. Additional blood samples will be collected for pharmacogenomics and exploratory biomarker evaluation.

Respiratory tract infection (RTI) surveillance will be conducted during the outpatient phase of the study from CRU discharge through the Day 120/165 outpatient visit or a lab-confirmed influenza infection, whichever occurs first. Subjects will be provided nasal/throat swab kits (for detection of influenza infection or other respiratory pathogen by a multiplexed polymerase chain reaction [PCR] test) and symptom diary cards.

If 3 or more RTI symptoms listed in the table below occur (at least one must be a respiratory symptom), subjects will contact study staff, then collect nasal/throat swab samples (the swabs should take place as soon as possible after the start of symptoms, ideally within 48 hours, but no later than 5 days). Subjects will complete symptom diary cards every 7 days to capture the worst grade of symptoms that occurred during the previous week. The Investigator/study staff will arrange for prompt shipment of the nasal/throat samples to the testing laboratory. Note: If the reported symptoms are already of a level of severity that urgent care is indicated, the subject should be directed to the appropriate facility to receive this care (e.g., emergency room). Otherwise, symptoms should be treated according to standard of care.

If an influenza infection is confirmed by the testing laboratory before the Day 120/165 outpatient visit, the event should be documented until all symptoms have resolved, including completion of the symptom diary card every 7 days. Thereafter, no further RTI surveillance will be carried out on the subject.

If the nasal/throat swab samples are not confirmed to be influenza by the testing laboratory, diary card completion will continue through the Day 120/165 outpatient visit.

Re	Respiratory Tract Infection (RTI) Symptoms				
•	Runny nose (rhinorrhea)	•	Shortness of breath (dyspnea)		
•	Stuffy nose (nasal congestion)	•	Wheeze		
•	Sore throat	•	Chilliness/feverishness or temperature ≥100°F		
•	Earache	•	Headache		
•	Cough	•	Body ache		
•	Productive phlegm/sputum				

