9.9. Adverse Events

Information on AEs (event term, start and stop dates, severity, relationship to blinded study drug) will be collected from the time of signing the informed consent form (ICF) until the final study visit after the dose of study drug. See Section 11 for additional information.

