12.6. Analyses of Respiratory Tract Infections

The number and percentage of subjects with any RTI will be provided.

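### TEAE and RTI percentages are counted to Day 120 at 50 mg but to Day 165 at 150 and 450 mg, so the dose columns are not like-for-like

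*Protocol*

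**What the plan says.** Section 12.3 defines a TEAE as an event that first appears during or after dosing, or "worsens relative to the pre-treatment state, and through the final study visit". The synopsis repeats this. Incidence is then tabulated by SOC and PT, relationship and severity.

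When the final visit falls depends on the cohort. Footnote a to the Schedule of Events (section 1.1) reads: "The timing of this visit is Day 120 for Cohort 1 and Day 165 for Cohorts 2 and 3". The visit window is ±14 days. Cohort 1 receives 50 mg, Cohort 2 150 mg and Cohort 3 450 mg, each with 7 active and 2 placebo subjects.

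RTI surveillance (section 6.1) runs "from CRU discharge through the Day 120/165 outpatient visit or a lab-confirmed influenza infection, whichever occurs first". Subjects stay in the unit "for observation and safety assessments from Day -1 (check-in) to Day 14", so surveillance starts at Day 14. Section 12.6 gives the whole RTI analysis: "The number and percentage of subjects with any RTI will be provided".

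Section 12 sets the columns: "All data will be summarized separately by dose level and study drug (CD388 Injection or placebo"). Sections 12, 12.3 and 12.6 name no common cut-off and no adjustment for length of observation.

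**The concern.** A crude percentage of subjects with at least one event rises with time observed. Here time observed is tied to dose: shortest at the lowest dose, longer at the two higher ones. In an ascending-dose study, readers scan the TEAE table from left to right for a rise with dose, and TEAE incidence and severity belong to the primary endpoint. Background illness alone would be expected to put a step between 50 mg and the other two columns, and that step could be read as a dose effect.

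For RTI the bias matters in the other direction. The exploratory objective is whether CD388 affects influenza-like illness, and longer surveillance at the higher doses could mask a fall with dose.

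The longer follow-up is not itself a fault. The difficulty is that the protocol fixes a counting window that differs by cohort and then places the resulting crude percentages side by side.

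**Working it through.** The protocol gives no event rate, power or precision figure for these summaries, so there is no stated figure to reproduce.

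**Inputs from the protocol**
- Final visit: Day 120 ± 14 (Cohort 1) and Day 165 ± 14 (Cohorts 2 and 3), section 1.1.
- RTI surveillance starts at Day 14, section 6.1.
- 7 active and 2 placebo subjects per cohort, section 6.1, Table 3.

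**Observation time**

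| | 50 mg | 150 and 450 mg | Ratio |
|---|---|---|---|
| TEAE, nominal | 120 days | 165 days | 165/120 = 1.375 |
| RTI, nominal | 120 − 14 = 106 days | 165 − 14 = 151 days | 151/106 = 1.42 |
| Permitted final visit | Days 106–134 | Days 151–179 | no overlap |
| TEAE, window extremes | 134 or 106 | 151 or 179 | 151/134 = 1.13 to 179/106 = 1.69 |
| RTI, window extremes | 120 or 92 | 137 or 165 | 137/120 = 1.14 to 165/92 = 1.79 |

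Because the permitted windows do not overlap, visit timing cannot close the gap for subjects who complete within window. If placebo were pooled, the six subjects would average (2 × 120 + 4 × 165)/6 = 150 days for TEAEs, which matches no dose column.

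**Size with no drug effect, constant hazard**

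If the risk at 50 mg is p1 and the higher doses are watched r times as long, their risk is p2 = 1 − (1 − p1)^r. The values of p1 are assumptions.

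| p1 at 50 mg | TEAE p2 (r = 1.375) | Step; subjects in 7 | RTI p2 (r = 1.42) | Step; subjects in 7 |
|---|---|---|---|---|
| 20% | 26.4% | 6.4 points; 0.45 | 27.2% | 7.2 points; 0.51 |
| 30% | 38.8% | 8.8 points; 0.61 | 39.8% | 9.8 points; 0.69 |
| 50% | 61.4% | 11.4 points; 0.80 | 62.7% | 12.7 points; 0.89 |

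Subjects in 7 is 7 × (p2 − p1), from unrounded values.

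The step has a ceiling whatever the background risk. With q = 1 − p1, q − q^r is largest at q = r^(−1/(r−1)), where it equals q(1 − 1/r). For RTI, q = 0.435 and the maximum is 0.435 × (1 − 106/151) = 0.130, or 0.91 of a subject. For TEAEs, q = 0.428 and the maximum is 0.428 × (1 − 120/165) = 0.117, or 0.82 of a subject.

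**TEAEs clustered soon after dosing**

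Suppose a share s of the Day-120 cumulative hazard falls before Day 28 and the rest is spread evenly over the remaining 92 days. The extra 45 days then give r = 1 + (1 − s) × 45/92.
- s = 0.50: r = 1.245; 20%, 30% and 50% become 24.2%, 35.8% and 57.8%.
- s = 0.75: r = 1.122; 20%, 30% and 50% become 22.2%, 33.0% and 54.1%.

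The step is then 2.2 to 7.8 points, or 0.15 to 0.55 of a subject in 7.

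**What is not affected**
- 150 mg against 450 mg, and each dose against its own cohort's placebo.
- The escalation review (at least 10 days) and the halting rules (28 days).
- Scheduled injection-site inspection, which ends by Day 6 in every cohort.
- Laboratory, ECG and vital-sign summaries by time point, unless Days 120 and 165 are merged into one row.

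**The case against.** The strongest objection is that the remedy is SAP material. An SAP is promised and not among the documents here; counting TEAEs to the last visit is proper safety capture; and nothing in the protocol forbids an extra table. All true, but the protocol does not leave the TEAE window open. It states a rule which, followed as written, makes follow-up differ with dose.

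Second, nothing planned turns on it. Safety is descriptive, no test across doses is specified, each cohort has its own placebo with identical follow-up, and pooling of placebo is not stated. This limits the consequences, and the pooled-placebo point is conditional. The 50 mg column will still be read against the other two, and with only 2 placebo subjects per cohort the within-cohort comparison offers little help.

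Third, the effect is small and the rates are assumed. At 20% to 50% risk, the standard deviation of a difference between two groups of 7 is √[(p1(1 − p1) + p2(1 − p2))/7], about 22 to 26 points, well above the step. Late events judged unrelated will also be identifiable in the tables by relationship. Both points stand and keep the severity moderate, but noise does not remove a shift in a known direction.

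Fourth, cohorts start one after another, so calendar season may outweigh or reverse the RTI effect. This stands. The RTI figures show the effect of surveillance length alone.

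**Conclusion.** The concern holds. As written, the protocol compares 120 with 165 days for TEAEs and 106 with 151 days for RTIs whenever 50 mg is set beside a higher dose. That part rests only on the document.

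The size in percentage points rests on assumed background risks of 20% to 50%, equal hazard at every dose, full follow-up and nominal visit days. TEAEs under a constant hazard give the upper end of their range; early clustering gives the lower end. The RTI range takes no account of season.

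This is a modest, directional distortion in the tables of a primary endpoint. It should be corrected because doing so is nearly free, but it undermines no planned decision.

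**What to change.** Add one sentence to each of sections 12.3 and 12.6, with matching synopsis text, along these lines:

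> In tables that compare dose levels or pool placebo, TEAEs (RTIs) with onset through Day 106 will be counted for all cohorts. Full-follow-up tables and listings will also be presented, with events per person-time and days of observation for each group.

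Day 106 is the last day that every subject who completes within window is certain to reach. It gives all cohorts 106 − 14 = 92 days of RTI surveillance. Day 120 would also remove the nominal difference, but a Cohort 1 subject seen as early as Day 106 would not be covered to Day 120. The person-time rates deal with early withdrawals and with RTI surveillance that stops at confirmed influenza.

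The cost is one extra set of tables and no new data. Section 9.9 already states: "Information on AEs (event term, start and stop dates, severity, relationship to blinded study drug) will be collected". The Schedule of Events footnote brings influenza-like illness into the same record: "Adverse events (including influenza-like illness which will be tested for both COVID-19 and flu) will be collected for all subjects".

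The drawback is that events after Day 106, including up to 14 days nominally shared by all cohorts (106 to 120), appear only in the full-follow-up tables and listings. Differences in season between cohorts remain and should be noted beside the RTI table.

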12.4. Pharmacokinetic Analyses

Based on the individual plasma concentration-time data, using the actual sampling times (see Schedule of Events, Table 1), the following PK parameters will be included:

- maximum plasma concentration (C_{max})
- time to maximum plasma concentration (T_{max})
- terminal elimination half-life $(t_{1/2})$
- apparent clearance (CL/F)
- apparent volume of distribution (V_Z/F)
- area under the plasma concentration-time curve from time 0 to time of last quantifiable sample (AUC_{0-last})
- area under the plasma concentration-time curve from time 0 extrapolated to infinity $(AUC_{0-\infty})$

CD388 concentration in the upper respiratory tract will also be determined.

Pharmacokinetic parameter estimation will be performed by non-compartmental analysis (NCA) with Phoenix® WinNonlin® version 8 or higher. The actual elapsed sampling times relative to dosing will be recorded during the study and will be used in the NCA analysis. Pharmacokinetic data handling and analysis will be further detailed in the SAP.

Descriptive statistics will be calculated for plasma concentrations at each individual time point and for all PK parameters. Mean and individual plasma concentration-time profiles will be presented graphically. Inferential statistics will also be conducted for log transformed PK exposure parameters versus historical control data in Western subjects from Study CD388.IM.SQ.1.01.

Pharmacokinetic samples for CD388 from this study may also be included in a population PK analysis, which will be reported separately.

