1. PROTOCOL SYNOPSIS

Sponsor: Cidara Therapeutics Inc., San Diego, CA

Product Name: CD388 Injection

Active Ingredients: CD388

Protocol Title: A Phase 1, Randomized, Double-Blind, Single Ascending Dose Study to Determine the Safety, Tolerability, and Pharmacokinetics of CD388 Subcutaneous Administration in Healthy Japanese Subjects

Planned Study Centers: Single center in the United States

Phase of Development: 1

Indication: Influenza virus infection

IND Number: 155,536

Objectives and Endpoints

Objectives	Endpoints
Primary	
To determine the safety and tolerability profile of CD388 Injection when dosed by subcutaneous (SQ) administration as a single dose to healthy Japanese adult subjects.	• Incidence and severity of treatment-emergent adverse events (TEAEs), including but not limited to adverse events (AEs) and serious adverse events (SAEs) (including systemic reactogenicity/injection site reactions and hypersensitivity reactions), AEs leading to study drug discontinuation and/or study withdrawal, vital signs, 12-lead electrocardiograms (ECGs), and clinical laboratory tests (including hematology coagulation, serum chemistry, and urinalysis), after a single dose of CD388.
Secondary	
To determine the plasma pharmacokinetic (PK) profile of CD388 Injection when dosed by SQ administration as a single dose to healthy Japanese adult subjects.	• Pharmacokinetic parameters following CD388 Injection administration: maximum plasma concentration (C _{max}), time to maximum plasma concentration (T _{max}), terminal elimination half-life (t _½), apparent clearance (CL/F), apparent volume of distribution (V _Z /F), area under the plasma concentration-time curve from time 0 to time of last quantifiable sample (AUC _{0-last}), area under the plasma concentration-time curve from time 0 extrapolated to infinity (AUC _{0-∞}).
Exploratory	
• To evaluate the PK profile of CD388 in upper respiratory tract after SQ administration as a single dose to healthy Japanese adult subjects.	• Pharmacokinetic parameters following CD388 Injection administration: maximum nasopharyngeal (NP) concentration (C _{max}), time to maximum NP concentration (T _{max}), area under the NP concentration-time curve from time 0 to time of last quantifiable sample (AUC _{0-last}).

Objectives	Endpoints
Exploratory (continued)	

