Safety, tolerability, and PK will be summarized using descriptive statistics. There will be no formal hypothesis testing. Analysis populations are:

- Safety Population: all subjects who receive any amount of study drug
- PK Analysis Population: all subjects who receive CD388 Injection and who have any blood samples analyzed

A Statistical Analysis Plan (SAP) will be prepared and finalized before unblinding for the first interim analysis. Any deviations from the final SAP will be described and justified in the study report. All statistical analyses will be performed using SAS®.

Descriptive statistics, including the numbers and percentages for categorical variables, and the numbers, means, standard deviations, medians, minimums, and maximums for continuous variables, will be provided. All data will be summarized separately by dose level and study drug (CD388 Injection or placebo). Listings of individual subject data will also be produced.

Safety will be evaluated by presenting summaries of AEs and SAEs, ECGs, clinical laboratory evaluations (hematology, coagulation, serum chemistry, urinalysis), and vital signs. Adverse events will be coded using the Medical Dictionary for Regulatory Activities (MedDRA). The incidence of TEAEs and AESIs will be presented by System Organ Class (SOC) and Preferred Term (PT), relationship to study drug, and severity. A TEAE is defined as an AE that emerges during or after study drug administration having been absent pre-treatment, or worsens relative to the pre-treatment state, and through the final study visit. In addition, the incidence of serious TEAEs and TEAEs leading to discontinuation of study drug or from the study will be presented by SOC and PT. Descriptive statistics for clinical laboratory test results, ECG parameters, and vital signs, and for changes from Baseline, will be presented by time point. The incidences of potentially clinically significant (PCS) clinical laboratory results, ECG parameters, and vital signs will also be summarized by time point.

A summary of the injection site evaluation will be presented. The number and percentage of subjects with any local reaction will be provided, as will the number and percentage of subjects with pain, tenderness, erythema/redness, and induration/swelling. The severity of each local reaction will also be presented.

The number and percentage of subjects with any RTI will be provided.

The PK parameters that will be assessed in the PK Analysis Population include:

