4.1.2.2. CD388 Clinical Studies

In an ongoing study (CD388.IM.SQ.1.01), the safety and tolerability of CD388 is being evaluated in Western healthy adult subjects, examining CD388 administered either intramuscularly or subcutaneously.

Regular assessment of blinded safety/tolerability data from 33 healthy subjects who received a dose of 50 mg, 150 mg, or 450 mg of subcutaneous CD388 or placebo has not identified any concerning safety observations to date.

All treatment-emergent adverse events (TEAEs) have been Grade 1 or Grade 2 (mild or moderate) in severity, with headache being the most frequently occurring (27.3% subjects), none of which occurred in the higher dose group (150 mg) as of the first Interim Analysis in the FIH study. Since then, preliminary safety data generated from the 450 mg dose group indicated that the safety and tolerability profile remained unchanged.

Of note, as of the first interim analysis in the FIH study, all TEAEs in the higher dose group (150 mg) have been Grade 1. No serious adverse events (SAEs) have occurred, and no drug-related TEAEs have resulted in clinically significant hematology or chemistry laboratory abnormalities. No safety issues associated with electrocardiograms (ECGs), vital signs, or physical examination findings (including local injection site reactions) have been identified. No safety findings have resulted in discontinuation or study drug or withdrawal from study. Preliminary safety data generated from the 450 mg dose group indicated that the safety and tolerability profile remained unchanged.

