4.5. Rationale for Trial Endpoints

The measures for evaluation of the safety and tolerability profile of CD388 Injection are standard for most clinical studies and follow the recommendations in the ICH guidelines. The assessments for determining the plasma concentrations are appropriate to characterize the pharmacokinetic (PK) profile of CD388.

Exploratory biomarkers, anti-drug antibodies, and pharmacogenomic research are exploratory in nature and do not have pre-defined endpoints.

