12.8. Determination of Study Sample Size

A total of 27 subjects will be enrolled in this study, with 21 of these subjects to receive CD388 Injection and 6 to receive placebo. The number of subjects was selected to allow sufficient evaluation of safety and tolerability, and PK, and is consistent with standards of practice for Phase 1 ethnic bridging studies.

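### Does the inferential PK comparison with Western subjects in Section 12.4 contradict the promise of descriptive statistics without formal testing?

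*Protocol*

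**What the plan says.** The Statistical Methods part of the synopsis states: "Safety, tolerability, and PK will be summarized using descriptive statistics. There will be no formal hypothesis testing". The opening of Section 12 repeats both sentences.

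Section 12.4 describes the non-compartmental analysis and the descriptive summaries of concentrations and parameters. It then adds: "Inferential statistics will also be conducted for log transformed PK exposure parameters versus historical control data in Western subjects from Study CD388.IM.SQ.1.01". The same section says: "Pharmacokinetic data handling and analysis will be further detailed in the SAP". Section 12 requires the SAP to be final before unblinding for the first interim analysis.

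The secondary PK objective, in the synopsis and in Section 5, is confined to Japanese subjects: "To determine the plasma pharmacokinetic (PK) profile of CD388 Injection when dosed by SQ administration as a single dose to healthy Japanese adult subjects". Section 6.1 gives the aims as "The goals are to assess safety, tolerability, and PK of CD388". The endpoint rationale in Section 4.5 says only: "The assessments for determining the plasma concentrations are appropriate to characterize the pharmacokinetic (PK) profile of CD388". None of these mentions Western subjects.

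Section 12.8 says the number of subjects was chosen to allow safety, tolerability and PK to be evaluated, and adds that it "is consistent with standards of practice for Phase 1 ethnic bridging studies".

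**The concern.** A reader who takes the general sentences as the whole PK plan finds an inferential commitment in 12.4 that they do not mention. The commitment is firm: the comparison will be done, whereas the population PK analysis in the same section is only a possibility. It has no objective or endpoint of its own and is missing from the synopsis methods. Yet 12.8 appeals to bridging practice, and this is the only Japanese/Western comparison to which the protocol commits.

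The term *inferential statistics* covers both tests and intervals. If the comparison were run as a significance test with 7 Japanese subjects per dose, a non-significant result could be taken as evidence of similar exposure when the data were merely sparse. An interval would show what the data can and cannot exclude. So the reading chosen could affect how the result is understood.

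**Working it through.** **1. The passages side by side.**

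| Place | What it provides |
|---|---|
| Synopsis, Statistical Methods | Descriptive PK summaries; no formal hypothesis testing |
| Section 12, opening | The same two sentences |
| Section 12.4 | Descriptive PK summaries, then inference on log exposure versus Western subjects; further detail in the SAP |
| Sections 5 and 6.1 | PK profile in Japanese subjects; no comparison named |
| Section 12.8 | Size set for safety, tolerability and PK, and in line with bridging practice |

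The opening of Section 12 does not say that PK will be summarised *only* descriptively. Section 12.4 says inference will *also* be done, directly after the descriptive statistics, so it adds to them. The bar on formal hypothesis testing stands at the head of Section 12 and applies to its subsections. Taken together: descriptive summaries, plus inference on log-transformed exposure that is not a formal test. Estimating a ratio with an interval satisfies every sentence.

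**2. The plan's own figure.** 3 cohorts × (7 + 2) = 27, of whom 3 × 7 = 21 receive CD388 and 3 × 2 = 6 placebo. This agrees with 12.8. The protocol states no power, margin or SD for the Western comparison, so there is no further figure to reproduce.

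**3. What a test would have done, if one had been planned.** The documents give neither the between-subject CV nor the number of Western subjects on CD388 per dose. Section 4.1.2.2 reports "33 healthy subjects who received a dose of 50 mg, 150 mg, or 450 mg of subcutaneous CD388 or placebo" in a study still under way, so that count includes placebo and is not final. Assumptions: CV 30% (range 20–40%), 8 Western active subjects per dose (range 6–12), true Japanese/Western ratio 1.25.

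- Log-scale SD: s = √ln(1 + CV²) = √ln(1.09) = 0.294.
- Standard error, one dose: 0.294 × √(1/7 + 1/8) = 0.152, with 7 + 8 − 2 = 13 degrees of freedom.
- 90% interval around an observed ratio of 1: exp(±1.771 × 0.152) = 0.76 to 1.31.
- Noncentrality for a ratio of 1.25: ln(1.25)/0.152 = 1.47. Power of a two-sided 5% t-test is 0.275, so 73% of trials would be non-significant.
- Three doses pooled, dose as a factor (21 vs 24; 45 − 4 = 41 degrees of freedom): standard error 0.0877, power 0.700.

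| CV | Per dose: non-significant | Per dose: 90% CI at ratio 1 | Pooled: non-significant | Pooled: 90% CI at ratio 1 |
|---|---|---|---|---|
| 20% | 48% | 0.83–1.20 | 4% | 0.91–1.10 |
| 30% | 73% | 0.76–1.31 | 30% | 0.86–1.16 |
| 40% | 82% | 0.70–1.42 | 53% | 0.82–1.21 |

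At CV 30%, varying the Western number from 6 to 12 per dose moves the per-dose non-significance rate from 76% to 67%, and the pooled rate (18 to 36) from 37% to 22%.

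**4. What these figures show.** The non-significance columns describe a formal test that Section 12 excludes. The interval columns depend only on the numbers of subjects and the CV, so they would be the same whether or not the wording changed. The range from 4% to 82% comes from the assumptions and from pooling, and is not a property of this protocol.

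**The case for a change.** The strongest case for a change is that objectives, and consistency between a protocol's own sections, belong in the protocol. A SAP cannot add a row to Section 5 or amend the opening of Section 12. If it specified a test, it would conflict with the bar on formal testing. The reader must supply the word *estimation*, because the protocol never uses it for this comparison. One clause would settle it at almost no cost.

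Part of this stands. The synopsis methods and the objectives do omit the comparison, and *formal* leaves some room for an informal p-value. Three things reduce its weight. First, the more harmful reading, a formal significance test, is already excluded. Second, the comparison uses exposure parameters that are already secondary endpoints. A supportive analysis of an existing endpoint does not need an objective of its own, and the possible population PK analysis has none either. Third, the sample size does not hang on the comparison: 12.8 first cites evaluation of safety, tolerability and PK, and mentions bridging practice in addition. The choice of parameters, interval level, reference groups and any weight adjustment is ordinary SAP content.

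**Conclusion.** No change to the plan is needed. The general sentences and Section 12.4 are compatible. Followed as written, the plan gives descriptive summaries plus a non-test comparison of log exposure, which analysts would ordinarily present as a geometric mean ratio with a confidence interval. Adding a clause would record that reading but would change no analysis, decision or precision. What remains is an editorial gap: the comparison is missing from the synopsis methods and the list of objectives.

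The conclusion rests on two points: that the exclusion of formal testing at the head of Section 12 governs 12.4, and that the SAP, which is not available here, sets out the comparison accordingly. If the SAP planned a significance test and read non-significance as similarity, that would conflict with Section 12 and would be a fault of the SAP. The power and interval figures rest on assumed values for the CV, the Western numbers and the 1.25 ratio, and serve only as illustration.
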